### 6.3. Effectiveness Outcomes

Descriptive analyses will include:

- Percent of cumulative CAILS score for index lesion as a proportion of the baseline CAILS score ([cumulative score at End of Study] / [cumulative score at Baseline] \* 100). The average, standard deviation and range of the %response at Week 10 will be summarized.
- Mean, standard deviation and range of the PGA score at End of Study.

- Mean, standard deviation and range of the mSWAT score at Baseline and End of Study.
- Mean, standard deviation and range of the change in the mSWAT score (calculated as the mSWAT score at End of Study – mSWAT score at Baseline).
- Mean, standard deviation and range of the Skindex 29 score and its 3 domains (emotions, symptoms, functioning) at Baseline and Week 8.
- Mean, standard deviation and range of the change in Skindex 29 score and its 3 domains.
- Mean, standard deviation and range of the VASitch score at baseline, each light treatment and the end of study visit.
- Shift analysis of VASitch categories (none/mild/moderate/severe) over all study timepoints.
- Mean, standard deviation and range for the treatment visit at which the maximum light dose was obtained.
- Mean, standard deviation and range for the maximum light dose that was used.
- Listing of changes of drug used (change in drug jar weight)

## 7. SAFETY ANALYSES

The safety analysis will be performed in all patients enrolled. Safety parameters include adverse events, laboratory parameters, vital signs, ECG parameters, and physical examinations.

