#### **5.3.2 Baseline**

After enrollment but prior to application of HyBryte the following assessments will be performed:

Interval medical history from screening obtained

Complete Physical Examination

Vitals taken (heart rate, respiratory rate, and sitting blood pressure)

Hematology panel drawn

Clinical chemistry panel drawn

Pregnancy test results reviewed

Three lesions that are representative of the patient's disease and are discrete with defined borders, will be chosen as the index lesions, and classified as patch or plaque lesions

Charting of all CTCL lesions on the "Body Lesion Diagram" form ([Appendix II](#)) locating and numbering each of the index lesion

Each of the index lesions will have a CAIIS score assessed and recorded

The mSWAT score will be assessed and recorded

5 mL of blood obtained and processed for serum hypericin levels

12-lead ECG obtained including QT interval measurements

The patient will complete the Skindex-29 ([Appendix III](#)) and VASitch forms and the data transcribed into the eCRF

A jar of ointment will be issued and the weight of the jar prior to dispensation will be recorded

Only after all of the above have been completed, patients will be instructed on proper drug application and demonstrate proficiency in drug application and all accessible lesions will be treated with study drug

The weight of the jar after drug application will be recorded

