#### **5.4 Premature Discontinuation**

Patients have the right to withdraw from this trial at any time (as described in the informed consent document) without prejudice to further care. An investigator may withdraw a patient from the study at any time for any of the following reasons:

- The patient withdraws his/her consent or refuses follow-up evaluations.
- The patient is lost to follow-up and will not attend further study visits.
- The investigator determines that further participation would be detrimental to the patient's health or well-being.
- The patient fails to comply with the study requirements so as to cause harm to self or seriously interfere with the validity of the study results.
- The female patient becomes pregnant during the treatment period. In this case, treatment should be halted and the patient followed until the end of the pregnancy. If a child is born, the infant should be followed through at least 6 months of age.
  - At the discretion of the site investigator if he/she feels that it is in the best medical interest of the patient.

Patients withdrawn from the study will have as many of the trial assessments completed as the patient permits including blood tests and lesion evaluations.

Patients withdrawn from the study may be replaced up to a total of 8 subjects provided that both the PI and the Soligenix Medical Monitor agree that the reasons for withdrawal do not suggest a change in the risk assessment of the HyBryte therapy.

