### 5.2. Analysis Populations

The analysis population is the Intent-to-Treat (ITT) population defined as all patients enrolled. All patients enrolled will be reported for all periods in which they have data available.

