### 5.3. Methodology and Conventions

All safety endpoints will be analyzed using all enrolled patients.

Lab results obtained from the local laboratories, will be used for all safety analyses. All analyses will be performed using SAS® Version 9.4 or higher.

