### 7.1. Adverse Events

Summary tables will be provided for all treatment-emergent adverse events (TEAEs). Treatment-emergent AEs are defined as events whose onsets occur, or severity worsens on or after the date of first dose of study drug. All TEAEs will be included in summaries.

An overview table will contain the number and percentage of patients with any TEAEs, with study drug related TEAEs, serious adverse events (SAEs), with AEs causing death, with related AEs causing death, with related SAEs, with AEs causing study drug discontinuation, and with AEs causing discontinuation from the study.

The TEAE summary tables will include counts of patients. Therefore, if a patient experiences more than one episode of a particular TEAE, the patient will be counted only once for that event. If a patient has more than one AE that is coded to the same preferred term, the patient will be counted only once for that preferred term. Similarly, if a patient has more than one TEAE within a SOC, the patient will be counted only once in that SOC.

All AEs are to be reported from the time of first administration of study drug until study completion or discontinuation. The severity of all AEs is recorded as mild, moderate, or severe. If severity is missing for TEAE, it will be set to severe. If severity is missing for AE at pre-treatment, the severity will be set to mild: if severity change is not reported during the study, then severity of mild is retained for analysis. A treatment-related AE is defined as an AE with relationship to study drug recorded as related or missing in the CRF. All AEs will be coded using the MedDRA (Version 10.1).

The maximum severity of AE is defined as the AE with the worst severity experienced overall during the study, within a SOC, or within a preferred term.

The following TEAE summaries will be presented:

- Frequency of TEAEs by preferred term, sorted by decreasing overall total
- Frequency of TEAEs related to study drug, by SOC and preferred term
- Frequency of TEAEs related to study drug by preferred term, sorted by decreasing overall total
- Frequency of TEAEs by maximum severity, SOC, and preferred term
- Frequency of AEs causing discontinuation from the study drug and study by SOC and preferred term
- Frequency of SAEs by SOC and preferred term
- Frequency of TEAEs with seriousness of fatal by SOC and preferred term.

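### The safety set is all enrolled patients, so any patient enrolled but never dosed would lower the percentages in the adverse event overview table

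*SAP*

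**What the plan says.** **Denominator.** SAP 5.2 defines a single population: "The analysis population is the Intent-to-Treat (ITT) population defined as all patients enrolled". SAP 5.3 applies it to safety: "All safety endpoints will be analyzed using all enrolled patients". SAP 7 repeats it: "The safety analysis will be performed in all patients enrolled". Section 5.2 adds that "All patients enrolled will be reported for all periods in which they have data available". None of these sections requires a dose.

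**Numerator.** SAP 7.1 reads: "Treatment-emergent AEs are defined as events whose onsets occur, or severity worsens on or after the date of first dose of study drug". The same section starts AE reporting at the first administration of study drug.

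**Order of events.** Protocol 5.3.2 introduces the Baseline procedures with "After enrollment but prior to application of HyBryte the following assessments will be performed". Dosing closes the list: "Only after all of the above have been completed, patients will be instructed on proper drug application".

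**Numbers.** Protocol 5.1 plans about 6 subjects. Protocol 5.4 adds that "Patients withdrawn from the study may be replaced up to a total of 8 subjects", provided that the investigator and the medical monitor agree that the reasons for withdrawal do not change the risk assessment.

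**The concern.** The two halves of an AE percentage rest on different conditions. Entering the numerator needs a first dose; entering the denominator needs only enrolment. Between the two lie the Baseline procedures, which include an interval history, a physical examination and review of the pregnancy test result, any of which could in principle stop a patient from being dosed. Such a patient could be withdrawn and replaced, and would still be counted.

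Assessing safety is a stated objective (Protocol 2.2, SAP 2.2), and the mismatch can act in one direction only: it lowers AE rates. That runs against the SAP's own cautious handling of AEs after dosing, where a missing severity becomes severe and a missing causality becomes related (SAP 8.1 and 8.2). With 6 to 8 patients, a single person in the denominator moves a percentage visibly.

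**Working it through.** The plan has no figure to reproduce. SAP 5.1 calls the sample size arbitrary, and neither document gives an expected AE rate or an expected number of undosed patients.

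**Step 1: which summaries are exposed.**

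| Summary | Rule in the SAP | Diluted by an undosed patient? |
|---|---|---|
| AE overview table (7.1) | Numbers and percentages; safety set is all enrolled | Yes |
| Other TEAE tables (7.1) | Described as counts of patients | Counts unchanged |
| Laboratory percentages (7.2) | Limited to subjects with a non-significant baseline value and a later assessment | No, if the patient has no later value |
| ECG criteria (6.1.2) | Number of patients at each timepoint | No |
| Vital-sign shifts (7.3) | Numbers of patients | No |

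The exposure is therefore the overview table, which carries the headline rates: any TEAE, related TEAEs, SAEs, deaths and discontinuations.

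**Step 2: inputs.**
- N, patients enrolled: 6 (Protocol 5.1) or 8 (the ceiling in Protocol 5.4).
- u, patients enrolled but never dosed: not given. Assumed to be 0, 1 or 2.
- x, patients with the event, all necessarily among the N − u who were dosed.

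**Step 3: formulas.**
- Percentage as planned: x / N.
- Percentage among dosed patients: x / (N − u).
- Ratio of the first to the second: (N − u) / N, which does not depend on x when x > 0.

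**Step 4: results.**

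| N | u | Ratio (N − u)/N | Example: dosed → as planned |
|---|---|---|---|
| 6 | 0 | 6/6 = 1.000 | no change |
| 6 | 1 | 5/6 = 0.833 | 1/5 = 20.0% → 1/6 = 16.7% |
| 6 | 2 | 4/6 = 0.667 | 1/4 = 25.0% → 1/6 = 16.7% |
| 8 | 0 | 8/8 = 1.000 | no change |
| 8 | 1 | 7/8 = 0.875 | 1/7 = 14.3% → 1/8 = 12.5% |
| 8 | 2 | 6/8 = 0.750 | 3/6 = 50.0% → 3/8 = 37.5% |

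For N = 6 and u = 1, the loss runs from 20.0 − 16.7 = 3.3 percentage points (x = 1) to 100.0 − 83.3 = 16.7 points (x = 5, every dosed patient affected). Rows with no events stay at zero whatever the denominator.

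**The case against.** The strongest reply is that the situation may never arise. Entry criteria are assessed and the pregnancy test is taken at Screening (Protocol 5.3.1). The 28-day screening window is counted to enrolment in Protocol 4.2 and to the Baseline visit in 5.3.1, which suggests that the two coincide. The first application closes the Baseline procedures. No entry criterion sets an ECG or laboratory threshold, and Protocol 5.3.2 requires only that those assessments be done. Neither document reports or expects an undosed patient. This stands: such a patient is possible but unlikely.

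A second reply is that any effect would be easy to see. Per-patient listings (Protocol 10.2), a listing of all AEs (SAP 7.1) and a frequency table of applications and light treatments (SAP 7.4) would expose a patient with no exposure, and a reader could recompute the rate. No decision rule uses an AE percentage. This also stands and limits the weight of the point, but a reader should not have to correct a headline table.

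A third reply is that SAP 5.2 reports patients only for periods with data. This does not settle the matter: the sentence is not written as a denominator rule for AE percentages, and an undosed patient may well have Baseline data.

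A reader might go further and infer that every AE percentage is diluted, or that laboratory, ECG and vital-sign results are too. The documents do not support that. Dilution needs at least one undosed patient, percentages are explicit only for the AE overview table, and the other summaries are protected as shown in the working.

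**Conclusion.** The mismatch is real, and nothing elsewhere in the SAP corrects it. Its effect is conditional and confined to the AE overview percentages. If every enrolled patient is dosed, the effect is zero. If one of 6 is not, those percentages are understated by a sixth (1 − 0.833).

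A reader might take the 25% relative understatement at 2 of 8 (1 − 0.750) as the expected size. It is not: it requires both replacement places to arise from patients who were never dosed, and Protocol 5.4 concerns withdrawals in general. All non-zero figures rest on assumed numbers of undosed patients. The point is modest in size, but it concerns a stated rule that can only bias the headline AE rates downward.

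**What to change.** In SAP 5.2, define a Safety population: all patients who received at least one application of HyBryte. In 5.3, 7 and 7.1, name it as the denominator for AE percentages. Keep all enrolled patients for disposition and for listings, so that anyone enrolled but not dosed remains visible. The laboratory, ECG and vital-sign rules need no change on this account.

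The cost is one definition and matching edits to three sections. No data are added. The SAP's Introduction places sign-off before database lock, which is when the change belongs. If every enrolled patient is dosed, the two populations are identical and no result changes.

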### **1.1.2      *Hypericin***

Hypericin is a natural compound found in the stems and petals of plants of the genus *Hypericum* (15-17). HyBryte™ is chemically synthesized hypericin formulated for topical application and not extracted from plants.

Hypericin is an effective virucidal agent that directly inactivates a broad range of viruses, including retroviruses (18-23), both as a stand-alone drug (24, 25) and after photoactivation (22, 26-29). Based on these promising *in vitro* virucidal effects, the compound was clinically evaluated for its utility in the management of human immunodeficiency virus (HIV) (30) and hepatitis C infections (31). However, no convincing evidence of clinical effectiveness as an antiviral was observed in these studies up to toxicity-limited doses, which were exclusively phototoxicity related.

In addition to its antiviral activity, hypericin has been shown in animal models to accumulate selectively in cancer cells up to a ratio of 12:1 cancer to healthy cells (32, 33). Again, hypericin appears to have tumoricidal effects both as a stand-alone drug (34-37) and after activation with visible light (15, 38-45). A clinical trial of parenteral synthetic hypericin for the treatment of brain gliomas found the drug to be safe and 10 of the 41 treated patients were considered treatment responders (46).

Although the information from these parenteral clinical trials is not directly applicable to the evaluation of the topical formulation of synthetic hypericin (HyBryte), the systemic doses of the drug were safe and at blood levels many magnitudes higher than expected following topical administration.

The dose-limiting toxicity in the systemic hypericin clinical trials was phototoxicity. The existence of this photoactivity, however, forms a basis for considering hypericin as an agent in topical phototherapy. *In vitro* studies with T-cells showed that hypericin could inhibit induced proliferation and near complete apoptosis in malignant CTCL T-cells with substantially less effects on normal T-cells similarly treated (47) and induced the inhibition of cell proliferation in adult T-cell leukemia cell lines with minimal effect on peripheral blood CD4+ T lymphocytes (48).

In general, it appears that the primary mechanism of the light-activated hypericin is through a Type II photoreaction. Hypericin localizes in the perinuclear region within the endoplasmic reticulum and Golgi apparatus (50, 51). When activated with visible light in

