### 3. STUDY DESIGN

This study is an interventional, uncontrolled, Phase 2a trial. Patients will receive treatments twice a week consisting of drug application followed 18 to 24 hours later with a light session (using Daavlin Series 7 Phototherapy Device with visible light lamps) for 8 weeks (up to 16 total treatments). The light treatment will be performed at least 2 calendar days apart each week. Light treatment is not permitted on consecutive days.

Blood samples for evaluation of serum hypericin concentration and ECGs will be obtained at Baseline, Week 4, Week 6, Week 8, and at End of Study. Safety laboratory tests and vital signs will be obtained at Baseline, at the end of treatment (Week 8), and at End of Study.

The light dose will be started at 5 J/cm^2 and may be increased each visit until symptoms or signs of mild phototoxicity (see [Table 1](#) for grading scheme) appear in the treated areas or until a maximum light dose of 25 J/cm^2 is reached, whichever occurs first.

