#### 4.4.10 Skin Reaction Safety Grading

Approximately 5 to 10 minutes before and after the completion of light therapy, treated lesions will be graded for erythema with the worst, best, and “average” scores recorded. The reaction will be graded using the definitions in [Table 6](#).

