**Table 10: Schedule of Assessments**

Time point	Blood Hypericin Concentration	ECG 	Light Session 	CAILS Evaluations	mSWAT	PGA	VAS itch	Skindex-29 QoL	Safety Assessments 	AE Collection
Screening 										
Baseline 	X 	X 		X 	X 		X 	X 	X 	
Week 1, Session 1			X				X			X
Week 1, Session 2			X				X			X
Week 2, Session 1			X				X			X
Week 2, Session 2			X				X			X
Week 3, Session 1			X				X			X
Week 3, Session 2			X				X			X
Week 4, Session 1			X				X			X
Week 4, Session 2	X  X 	X  X 	X				X			X
Week 5, Session 1			X				X			X
Week 5, Session 2			X				X			X
Week 6, Session 1			X				X			X
Week 6, Session 2	X 	X 	X				X			X

Time point	Blood Hypericin Concentration	ECG 	Light Session 	CAILS Evaluations	mSWAT	PGA	VAS itch	Skindex-29 QoL	Safety Assessments 	AE Collection
Week 7, Session 1			X				X			X
Week 7, Session 2			X				X			X
Week 8, Session 1			X				X			X
Week 8, Session 2 Drug Application	X 									X
Week 8, Session 2 Light Session	X  X 	X  X 	X				X	X	X 	X
Week 10/End of Study	X	X		X	X	X	X		X	X

 ECG will include a standard 12-lead reading with QT interval measurements. Correction for heart rate will be performed electronically using both the Bazett's and Fridericia formulas.

 Light Session: Includes application of drug 18-24 hours earlier by the patient and the Erythema Scoring performed 5-10 minutes before and after light therapy

 Safety Assessments: consists of vital signs, and hematology and clinical chemistry blood tests

 The following assessments will be performed at the Screening visit: Obtain Informed Consent Form (ICF) signature, Assessment of entry criteria, Complete Medical History, Complete Vital Signs, Serum HCG pregnancy test (women of childbearing age only)

 Baseline: Includes interval medical history from screening, Complete Physical Examination, review of the results of the serum pregnancy test for eligible female subjects, and charting of index lesions onto the Body Lesion Diagram.

 Obtained prior to drug application

 Prior to light session

 2 hours after completion of the light session

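### The skin reaction safety grade taken before and after every light session has no named output in the SAP, so reactions above the titration target reach a safety table only if reported as AEs

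*SAP*

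**What the plan says.** SAP 4.4.10 is titled "Skin Reaction Safety Grading". It says: "Approximately 5 to 10 minutes before and after the completion of light therapy, treated lesions will be graded for erythema". Worst, best and average scores are recorded on a scale from Grade 0 (no reaction) through mild, moderate and severe with edema to Grade IV (life-threatening). Protocol 6.11 and Table 11 describe the same measure. Footnote 2 of the SAP schedule (Table 10) makes it part of every light session: "Includes application of drug 18-24 hours earlier by the patient and the Erythema Scoring performed 5-10 minutes before and after light therapy". SAP 3 allows up to 16 treatments over 8 weeks.

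SAP 7 defines the content of the safety analysis: "Safety parameters include adverse events, laboratory parameters, vital signs, ECG parameters, and physical examinations". The skin grade is not in that list. SAP 7.1 to 7.4 cover adverse events, laboratory tests, vital signs and extent of exposure. SAP 6.3 summarises the maximum light dose and the visit at which it was reached.

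On background, Protocol 1.1.2 states: "The dose-limiting toxicity in the systemic hypericin clinical trials was phototoxicity". Safety of HyBryte photodynamic therapy is the secondary objective in Protocol 2.2 and is among the secondary objectives in SAP 2.2.

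**The concern.** The plan collects a graded local-tolerability measure at every session, calls it a safety grading, and then gives it no place in the safety analysis. Mild erythema (Grade I) is the level to which light is titrated, so what matters for safety is how often, and how far, patients went beyond it. As written, that information reaches a table only through adverse event reporting. No rule says which grade becomes an adverse event, in a treatment where some erythema is intended.

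Two things are at stake. The report may state a maximum light dose without saying whether it was reached at Grade I or with stronger reactions. And if someone does tabulate the grade, the choice among worst, best and average, among timepoints, and between per-session and per-patient summaries would be made after the data are seen.

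**Working it through.** The documents give no figure to reproduce: SAP 5.1 calls the sample size arbitrary. The check traces each measure from definition to output and then counts the data involved.

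**Step 1. Each measure in SAP 4.4 and its named analysis.**

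| Measure (SAP section) | Named output |
|---|---|
| ECG (4.4.1) | 6.1 |
| Hypericin (4.4.2) | 6.2 |
| Laboratory tests (4.4.3) | 7.2 |
| Vital signs (4.4.4) | 7.3 |
| Skindex-29 (4.4.5) | 6.3 |
| VAS itch (4.4.6) | 6.3, including every light treatment |
| CAILS (4.4.7) | 6.3 |
| PGA (4.4.8) | 6.3 |
| mSWAT (4.4.9) | 6.3 |
| Skin reaction grade (4.4.10) | none |

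Nine of ten have a named output.

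**Step 2. Do general provisions fill the gap?** SAP 5 says categorical data are summarised as counts, and Protocol 10.2 promises per-patient listings. Neither names the grade, says which of the three scores to use, or says how pre- and post-session values are to be handled.

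**Step 3. Volume of data without a named output.** Inputs: up to 16 sessions (SAP 3); 2 gradings per session and 3 scores per grading (SAP 4.4.10); about 6 patients (Protocol 5.1), or 8 with replacement (Protocol 5.4).

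- Gradings per patient: 16 × 2 = 32. Scores per patient: 32 × 3 = 96.
- 6 patients: 32 × 6 = 192 gradings; 96 × 6 = 576 scores.
- 8 patients: 32 × 8 = 256 gradings; 96 × 8 = 768 scores.

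These are maxima, because 16 is an upper limit on sessions. They measure data volume, not bias.

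**Step 4. What a table could support.** If none of n patients had a reaction of a given grade, the one-sided 95% upper bound on the patient rate is 1 − 0.05^(1/n). For n = 6 this is 39.3%, and for n = 8 it is 31.2%. The output would be descriptive only.

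**Step 5. What the pre-session grade measures.** It is taken 18 to 24 hours after a new drug application, on lesions inspected for pink drug staining (Protocol 5.3.3), in a disease whose lesions are themselves scored for redness (CAILS erythema subscore, Protocol Table 5). The Baseline procedures (Protocol 5.3.2) include no skin reaction grade. A raised grade on either side of a session can therefore include disease erythema or staining, so the post-session grade needs its paired pre-session value.

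**Step 6. Physical examinations.** SAP 7 lists them, but "Complete Physical Examination" is scheduled only at Baseline (Protocol 5.3.2; SAP Table 10, footnote 5), and SAP 7.1 to 7.4 plan no analysis of them. No scheduled on-treatment result exists to report.

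**The case against.** The strongest reply is that the score is mainly a titration tool. Protocol 5.3 and 6.1 use it to set the next light dose, the synopsis does not list it among the safety variables, and SAP 6.3 and 4.3 summarise the resulting light doses. Adverse events are asked about at every session, signs detected by the investigator count, and Grades I to III use the same severity words as the adverse event scale. A Grade IV reaction is labelled life-threatening, which is a serious adverse event criterion. Protocol 10.2 also tabulates adverse events within 48 hours of application, a window that includes the light session. The study is exploratory, with about 6 patients.

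Much of this stands. Part of the signal will be captured. But light-dose summaries do not report the reaction, SAP 4.4.10 itself labels the score a safety grading, and shared severity words do not say when a grade becomes an adverse event.

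Four stronger readings are tempting and are not supported:

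- *Phototoxicity is the known dose-limiting toxicity of HyBryte.* Protocol 1.1.2 says this of systemic hypericin, and calls the parenteral trial information not directly applicable to the topical product.
- *The grades will go wholly unanalysed.* The general wording in SAP 5 and Protocol 10.2 could lead to some output; what is missing is a named one.
- *Adverse event reporting will under-count.* That is an inference. In Protocol Table 2, Phase 3 patients did have erythema (7 of 161) and application site pain (16 of 161) recorded as adverse events. One unreported Grade III patient in six would change a rate from 1/6 = 17% to 0%, but no document figure makes this likely.
- *The pre-session grade shows a reaction persisting from the last treatment.* Step 5 of the working shows why it cannot be read that way.

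**Conclusion.** The gap is real and worth closing. The skin reaction grade is the only measure in SAP 4.4 without a named output, and the SAP 7 list of safety parameters omits it. Under the written plan, the safety objective depends on investigator-reported adverse events for reactions above Grade I, and light dose is reported apart from the response to it.

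The size is up to 32 gradings per patient and up to 192 in 6 patients, assuming full treatment and complete recording. No bias in an adverse event rate can be calculated from the documents. Neither primary endpoint is affected. This is an inexpensive improvement to a secondary objective that the plan should make; it does not invalidate the study. The physical-examination wording is clerical and changes no result.

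**What to change.** Add the skin reaction grade to the SAP 7 safety parameters and specify, using the recorded worst score:

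- for each session, the pre-session grade, the post-session grade and the within-session change;
- the number of patients by maximum post-session grade, and by maximum within-session increase;
- the number of patients with any post-session Grade II, III or IV, shown with the paired pre-session grade;
- a by-patient listing of these values with the light dose delivered at that session.

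State that the pre-session grade is not to be interpreted as a persisting reaction, because it follows a new drug application and may include disease erythema and drug staining. Label the change as a change in the patient's worst score, since the worst lesion before light need not be the worst after it.

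The cost is one table and one listing from scores that the plan already requires to be recorded, with no added patient assessment and no change to clinical procedures. First confirm that the scores are captured in the eCRF: Protocol 6.11 and SAP 4.4.10 say only that they are recorded. As an incidental tidy-up, mark physical examinations in SAP 7 as baseline only.
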